6.1.6. Pooling of Sites

All sites will be pooled together for analysis.

6.1.7. Derived Variables

- TPSS = sum of erythema (graded 0-4), thickness (graded 0-4), and scaling (graded 0-4) for each target plaque. The sum of TPSS scores of up to 3 target plaques within a visit will be used for analysis.
- TPA (cm^2) = the longest diameter (cm) of the target plaque multiplied by the widest perpendicular diameter (cm) (ie, perpendicular to the longest diameter of the target plaque). The sum of TPA (cm^2) of up to 3 target plaques within a visit will be used for analysis.
- TPSS x TPA = sum of TPSS x TPA of up to 3 target plaques within a visit. Note that TPSS x TPA is calculated for each target plaque before summing up the results for all plaques. If a plaque is resolved after baseline with a score of 0 for all descriptors for TPSS (ie, erythema, thickness, and scaling), TPSS x TPA will be recorded as 0.
- Cream used (g) in a tube = dispensed tube weight (g) – returned tube weight (g).
- Overall cream used (g) = sum of cream used in a tube over all tubes
- Number of doses of study drug = number of expected doses (number of days on study [including BID dosing on Days 1, 14, and 28], where number of days on study is derived as last treatment – first treatment + 1) minus total number of missed doses, as collected in the CRF. Add a 1 for each of the Day 1, 14, and 28 visits that are completed (meaning, study drug discontinuation did not occur until at least the next day; so if a subject finished the study, 3 doses would be added to the final amount).
- Percent compliance (for purposes of determining the PP Population as described in [Section 5](#)) = average of compliance as recorded in the eCRF, calculated as sum of [100% if “Was the subject compliant?” marked Yes in the eCRF or percent compliance as recorded in the eCRF comments when “Was the subject compliant?” is marked as No] / number of non-missing compliance records from the eCRF.
- Quick Inventory of Depressive Symptomatology-Self-Report (QIDS-SR) total score = (highest score on questions 1-4) + item 5 + (highest score on questions 6-9) + item 10 + item 11 + item 12 + item 13 + item 14 + (highest score on questions 15-16). The range for the QIDS-SR total score is 0 to 27.

- QIDS-SR severity level⁴:
 - No depression: total score ≤ 5
 - Mild depression: total score = 6 to 10
 - Moderate depression: total score = 11 to 15
 - Severe depression: total score = 16 to 20
 - Very severe depression: total score ≥ 21
- Change from baseline = value at current time point – value at baseline.
- Percent change from baseline = (change from baseline / baseline) * 100.
- TEAE = any AE with an onset date/time after first dose of study drug in each cohort.

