8.11 Treatments

8.11.1 Drug Administration

Cohort 1: ARQ-151 cream 0.5% will be applied by site personnel to 25 cm² of psoriatic plaque(s) (more than one plaque may be identified for a total area of 25 cm²).

The study sponsor or its representative will ensure the study staff can demonstrate proper dosing for Cohort 1 at the Site Initiation Visit. Study staff will be trained to ensure a unit dose (a pea-sized amount of ARQ-151 cream vehicle) is properly squeezed from the vehicle training tube and applied as a thin film and rubbed in using the index and middle finger, rubbing in thoroughly but gently, until the 'white' has disappeared.

Cohort 2: At the randomization visit, the study staff will demonstrate to the subject how to apply ARQ-151 cream or vehicle using the first tube from the kit that is assigned to the subject at randomization. The study staff will demonstrate application to the subject according to the technique described above. The subject will then practice squeezing a similar amount onto their index and middle finger and apply a thin film to areas to be treated. The study staff will confirm that the subject's application technique is correct.

Re-training will be conducted at subsequent visits (visits 3 and 5) as needed using a vehicle training tube (i.e., if a returned tube weighs substantially more or less than the expected weight).

Subjects will be instructed to apply study medication each evening at least 15 minutes after showering or bathing (if they take an evening shower/bath) and then to not wash areas where ARQ-151 cream or vehicle have been applied until the following morning. Study medication should be applied at least 10 minutes before going to bed.

Each study medication tube will be weighed prior to dispensing at the baseline visit and each follow up visit. Study medication tubes returned by subjects will also be weighed and compliance will be assessed. If the subject's actual use is substantially greater than or less than the expected use, the subject will retrained on the study drug application technique.

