9.1.2 Subjects to Analyze

Safety population will include all subjects who are enrolled and received at least one confirmed dose of study medication. This population will be defined separately for each cohort.

The Modified Intent-to-Treatment (mITT) population will include all subjects who are in the safety population for Cohort 2 with at least one post-baseline efficacy evaluation.

Per-Protocol (PP) Population will include all subjects who are in the safety population for Cohort 2, were at least 80% compliant with study medication, and showed no other serious deviations from the study protocol.

The PK population will include all subjects receiving the active drug with sufficient plasma concentrations of roflumilast to define a profile, as determined by the pharmacokineticist. This population will be defined separately for each cohort.

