4.2. Interim Analysis and Data Monitoring

No interim analyses are planned.

5. Analysis Populations

The following analysis populations are planned for this study:

- **Safety Population:** The Safety Population includes all subjects who are enrolled and received at least 1 confirmed dose of study medication in each cohort. This population will be defined separately for each cohort. Analyses using the Safety Population for either cohort will be based on treatment received.
- **Modified Intent-To-Treat (mITT) Population:** The mITT Population includes all subjects who are in the Safety Population for Cohort 2 with at least 1 post-baseline efficacy evaluation. Analyses using the mITT Population will be based on randomized treatment.
- **PK Population:** The PK Population includes all subjects, who consented to PK draws, receiving the active drug with sufficient plasma concentrations of roflumilast to define a profile, as determined by the pharmacokineticist. This population will be defined separately for each cohort. Analyses using the PK Population will be presented in a separate PK report, provided by the pharmacokineticist.
- **Per Protocol (PP) Population:** The PP Population includes all subjects who are in the Safety Population for Cohort 2, were at least on average 80% compliant with study medication, and showed no other serious deviations from the study protocol. Analyses using the PP Population will be based on randomized treatment.

6. General Issues for Statistical Analysis

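### The per-protocol compliance average in SAP 6.1.7 sets no upper limit on a record, so an interval marked non-compliant for overuse can offset underuse elsewhere

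*SAP*

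**What the plan says.** The protocol (9.1.2) admits to the PP population subjects in the Cohort 2 safety population who "were at least 80% compliant with study medication" and had no other serious deviations. SAP section 5 words the criterion as "were at least on average 80% compliant with study medication". The averaging is an addition to the protocol wording, and SAP section 10 does not list it as a change. Both documents give a lower bound only.

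SAP 6.1.7 supplies the formula. Percent compliance is the "average of compliance as recorded in the eCRF, calculated as sum of" one score per record. The score is 100 when the eCRF compliance question is answered Yes, and otherwise the "percent compliance as recorded in the eCRF comments when" the answer is No. The divisor is the "number of non-missing compliance records from the eCRF". No cap or truncation is stated.

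On measurement, Protocol 8.11.1 has returned tubes weighed and compliance assessed. It calls for retraining if the subject's "actual use is substantially greater than or less than the expected use". Protocol 8.11.3 adds a daily diary of doses applied and missed, which staff use when questioning the subject about compliance.

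SAP 8.1 bases the primary MMRM on the mITT population and repeats it on the PP population.

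**The concern.** A Yes record is fixed at 100, while a No record enters at whatever value was written. The protocol treats use well above the expected amount as a departure, in the same sentence as use well below it. If a site marks an overuse interval No and records, say, 140, the formula gives that departure more credit than an interval used as planned. The surplus then cancels a shortfall in another interval.

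At stake is who enters the PP repeat of the primary analysis. That repeat is meant to describe the effect in subjects who used the cream as intended. A subject could meet the 80% criterion only because a second departure was counted in their favour.

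**Working it through.** The plan gives no worked compliance figure to reproduce. The check applies its formula to example records.

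**Inputs**
- Threshold: mean of at least 80 (Protocol 9.1.2; SAP section 5).
- Score: Yes = 100; No = the percentage as written (SAP 6.1.7).
- Records per completer: four, at Visits 3 to 6. This is an assumption based on tubes being weighed at each follow-up clinic visit (Protocol 8.11.3). The eCRF is not in the documents.
- The record patterns are hypothetical.

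**Formulas**
- As written: mean = (sum of scores) / (number of non-missing records).
- Capped: the same, with each score replaced by min(score, 100).

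| Records | As written | Meets 80%? | Capped | Meets 80%? |
|---|---|---|---|---|
| 40, 40, 140, 100 | 320/4 = 80.0 | yes | 280/4 = 70.0 | no |
| 50, 50, 110, 110 | 320/4 = 80.0 | yes | 300/4 = 75.0 | no |
| 60, 140, 100, 100 | 400/4 = 100.0 | yes | 360/4 = 90.0 | yes |
| 60, 60, 100, 100 | 320/4 = 80.0 | yes | 320/4 = 80.0 | yes |
| 100, 100, 100, 20 | 320/4 = 80.0 | yes | 320/4 = 80.0 | yes |

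The first two rows show the effect. The second needs an excess of 10% to be marked No. If the site marks those intervals Yes, they score 100 and the mean is already 75.0.

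**General form.** Suppose two of four intervals average u and the other two average h. The criterion is (2u + 2h)/4 ≥ 80, so u ≥ 160 − h. The lowest admissible u is 60 when h = 100, 40 when h = 120, and 10 when h = 150. With a cap, h cannot exceed 100, so the floor stays at 60.

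**Other rules that might catch the case**
- Protocol 8.9.3 allows removal for interrupting more than 50% of scheduled doses, or for repeated failure to comply. Both are discretionary. If the recorded percentages are read as the share of doses applied, the shortfall in 40, 40, 140, 100 is (60 + 60 + 0 + 0)/4 = 30% of doses, below 50%.
- The exclusion for other serious deviations is not defined in terms of overuse.
- SAP 6.1.7 also derives a number of doses from missed doses, but the PP compliance rule does not use it.

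None of these reliably excludes the first two rows.

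**The case against.** The strongest objection is that the trigger is not visible. It needs a site both to mark an overuse interval No and to write a figure above 100. The protocol's stated response to overuse is retraining; it does not say that overuse is recorded as non-compliance or how it becomes a percentage. No expected weight in grams is given, nor a cut-off between Yes and No. If overuse is marked Yes, it already scores exactly 100. If the percentage is a diary count of doses, it cannot exceed 100. This stands: the documents show that the case is possible, not that it is common.

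Second, the formula carries out the SAP's own averaged criterion, and weekly tube weights carry error. A tube returned one visit late could give 60 then 140, where the true figure is 100 in both. A cap biases such a subject downward. The direction is right, but the consequence is small: 60, 140, 100, 100 still qualifies at 90%. The real cost is that a subject whose total use was at least 80% of expected can be excluded. If the intervals have equal expected use and the Yes record is taken as 100% use, the 40, 40, 140, 100 subject is one of these.

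Third, a reader might infer that the missing cap is what admits subjects under-treated for half the trial, or just before the Week 4 assessment. The documents do not support that. Averaging alone admits 60, 60, 100, 100 and 100, 100, 100, 20, and a cap changes neither. In 40, 40, 140, 100 the shortfall is in the first two weeks, not the last two. Nor can one say that surplus cream made up for missed days: a weight-based 40% may mean thinner daily application.

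**Conclusion.** The point holds as a gap in a stated rule. SAP 6.1.7 lets a non-compliant interval score above a compliant one, so recorded overuse can lift a subject from 70% or 75% to the 80% threshold in the examples shown. It rests on two assumptions: that some overuse intervals are marked No, and that the figure written for them exceeds 100. Protocol 8.11.1 makes this foreseeable, because it assesses compliance from tube weights and names use above expected as a departure.

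The size in this trial cannot be determined. It is zero if overuse is marked Yes or if percentages are diary-based. Any share of the PP population would depend on variability in use and marking habits for which the documents give no values, so none is offered.

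The consequence is limited to the supportive PP repeat of the primary MMRM. A reader might take it as a threat to the primary result, but that result is on the mITT population, whose definition does not involve compliance. This is a minor point, worth settling because the correction is easy.

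**What to change.** In SAP 6.1.7, score each No record as min(recorded percentage, 100) before averaging, and show recorded use above 100% separately in the compliance listing. Make the change before unblinding, so that PP membership does not depend on a later judgement about such records.

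The cost is one phrase in the SAP and one line of code. If no recorded value exceeds 100, nothing changes. Otherwise the PP population may be slightly smaller, and some subjects whose total cream use was at least 80% of expected may be excluded.

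The cap leaves averaging itself untouched. If the sponsor also wants to exclude patterns such as 60, 60, 100, 100, that needs a separate rule, such as a minimum per interval.

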3.1. Overall Design

There are 2 cohorts of subjects:

Cohort 1

Cohort 1 is an open label, single dose study to 25 cm² of psoriatic plaque(s) in up to up to 8 subjects with psoriasis. Cohort 1 subjects may then be enrolled into Cohort 2 of the study if all admission criteria are met at the Baseline Visit (Day 1, Visit 2, per Cohort 2). In this case, the same plaque(s) treated in the Cohort 1 study may also be treated in Cohort 2; however, a minimum of 14 days of wash-out is required between Cohort 1 drug application and the baseline visit of Cohort 2. This cohort involves a minimum of 3 clinic visits including Screening, Baseline, 1 follow-up visit (24 hours after the baseline visit) and 1 follow up telephone call 7 days after the follow up visit. Subjects may be asked to return for additional visits(s) if an adverse reaction occurs. The interval between the Screening and Baseline visits could be up to 14 days, therefore the anticipated maximum duration of subject participation in Cohort 1 is 22 days.

Cohort 2

Cohort 2 is a parallel group, double blind, vehicle controlled study in which ARQ-151 cream 0.5%, ARQ-151 cream 0.15% or vehicle cream is applied QD x 28 days to subjects with 0.5% to 5.0% BSA of chronic plaque psoriasis, inclusive. This cohort involves a minimum of seven clinic visits including Screening, Baseline and 4 visits at Week 1, Week 2, Week 3, and Week 4 of treatment and a Day 29 visit for a final PK collection. A follow-up telephone call with subjects will occur at Week 5 to assess any reactions to discontinuing drug product and will decide upon disposition of any ongoing AEs. The interval between the Screening and Baseline visits could be up to 6 weeks, therefore the anticipated maximum duration of subject participation in Cohort 2 is 77 days.

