7.4. Exposure and Compliance

The number of doses received by each subject based on diary data will be summarized by treatment for Cohort 2 subjects only, in both a continuous manner (using summary statistics) and a categorical manner (using number and percentages), presenting the following categories: 1 to 8 doses (up to 1 week of treatment); 9 to 15 doses (1-2 weeks of treatment); 16-23 doses (2-3 weeks of treatment); and 24 to 31 doses (3-4 weeks of treatment).

Similarly, the amount of study medication applied by each subject based on tube weight will be summarized by treatment for Cohort 2 subjects only, using summary statistics.

These analyses will be conducted for the Safety Population for each cohort.

AD-ST-33.04 Effective date: 30-Jun-2017

Drug application for each cohort, vehicle training application for Cohort 2, study medication dispensation and return weight, and missed doses will be presented in the listings.

8. Efficacy Analysis

Efficacy will be assessed for Cohort 2 only. Individual subject listings will be prepared for all efficacy data.

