13.1.1. Demographic Data

Table 5: Demographic Data Summary Tables

Number	Population	Title
Table 14.1.1	All Subjects	Summary of Subject Disposition by Treatment and Cohort
Table 14.1.2	Safety	Summary of Demographics and Baseline Characteristics by Treatment and Cohort
Table 14.1.3	Safety	Incidence of Medical Histories by SOC, PT, Treatment, and Cohort
Table 14.1.4	Safety	Summary of Prior Medications by ATC Class Level 4, PT, Treatment, and Cohort
Table 14.1.5.1	Safety	Summary of Study Drug Compliance using Doses Received by Treatment

AD-ST-33.04 Effective date: 30-Jun-2017

Statistical Analysis Plan,
Sponsor Arcutis, Inc.
Protocol Number ARQ-151-101
PCN Number ARCU7063

Table 14.1.5.2	Safety	Summary of Study Drug Compliance using Tube Weight (g) by Treatment
----------------	--------	---

Statistical Analysis Plan,
 Sponsor Arcutis, Inc.
 Protocol Number ARQ-151-101
 PCN Number ARCU7063

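### Per-protocol compliance is averaged over the eCRF records present and SAP 5 sets no minimum exposure, so an early stopper can score 100% and enter PP with under 80% of the planned doses

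*SAP*

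**What the plan says.** SAP Section 5 takes PP from the Cohort 2 Safety Population and requires that subjects were "at least on average 80% compliant with study medication, and showed no other serious deviations from the study protocol". Protocol 9.1.2 has the same 80% threshold without the averaging, and gives no base for the percentage.

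SAP 6.1.7 gives the formula, expressly for PP membership. Each eCRF compliance record marked Yes scores 100%, and each record marked No scores the percentage written in the comments. The sum is divided by the "number of non-missing compliance records from the eCRF". SAP 6.1.4 does not impute missing data beyond the conventions in 6.1.8, which concern dates and times.

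The same section derives a separate dose count. It counts days on study, "including BID dosing on Days 1, 14, and 28", less missed doses, and notes that "if a subject finished the study, 3 doses would be added to the final amount". SAP 3.1 describes the regimen differently: "vehicle cream is applied QD x 28 days to subjects with 0.5% to 5.0% BSA". SAP 7.4 uses the dose count for exposure categories that end at "24 to 31 doses (3-4 weeks of treatment"). SAP Table 14.1.5.1 reports it, for the Safety Population, as "Summary of Study Drug Compliance using Doses Received by Treatment". The PP formula does not use this count.

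SAP 8.1 bases the primary analysis on mITT and repeats it in PP.

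**The concern.** Records that never arise because a subject stopped treatment drop out of both the numerator and the denominator. One, two or three Yes records therefore all average 100%, however little of the 28-day course was taken.

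The only other PP filter is the absence of serious deviations. The SAP does not define that term: SAP 7.2 classes deviations as major or minor, and early discontinuation is not named as a deviation. The removal reasons in Protocol 8.9.3, which include interrupting more than half the scheduled doses, govern study participation and do not define PP.

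At stake is what the PP repeat of the primary analysis represents. A reader will take an 80% compliance criterion to describe subjects who received most of the treatment, and as written the set could include subjects well short of that.

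**Working it through.** **Inputs.** 80% threshold (SAP 5; Protocol 9.1.2). Record scoring and dose count (SAP 6.1.7). 28 treatment days (SAP 3.1). Exposure categories (SAP 7.4). Assumptions: one compliance record at each of Visits 3 to 6, no missed doses before stopping, and every existing record marked Yes.

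**Reproducing the plan's dose count.** Doses = last treatment day + 1 for each of Days 1, 14 and 28 that is completed.
- Full course: 28 + 3 = 31
- Last dose Day 7: 7 + 1 = 8
- Last dose Day 14: 14 + 1 = 15 (16 if the extra Day 14 dose is counted)
- Last dose Day 21: 21 + 2 = 23

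These match the upper ends of the SAP 7.4 categories, for example "9 to 15 doses (1-2 weeks of treatment").

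**SAP percent compliance for the same subjects.** Sum of scores / number of records: 100/1 = 200/2 = 300/3 = 100%. All pass 80%.

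**Share of the planned course.**

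| Last dose | 31-dose count | 28-dose count | SAP formula |
|---|---|---|---|
| Day 7 | 8/31 = 25.8% | 7/28 = 25.0% | 100% |
| Day 14 | 15/31 = 48.4% (16/31 = 51.6%) | 14/28 = 50.0% | 100% |
| Day 21 | 23/31 = 74.2% | 21/28 = 75.0% | 100% |
| Day 22 | 24/31 = 77.4% | 22/28 = 78.6% | 100% |
| Day 23 | 25/31 = 80.6% | 23/28 = 82.1% | 100% |

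On either count, any last dose up to Day 22 is below 80% of the planned course, and Day 23 is the first day above it.

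**Would a final No record exclude the subject?** With k Yes records and one No at x%, exclusion needs (100k + x)/(k + 1) < 80, that is x < 80 − 20k.
- k = 1: x < 60
- k = 2: x < 40
- k = 3: x < 20

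Two Yes records and one No at 50% give (100 + 100 + 50)/3 = 83.3%, which passes. Two Yes and two No at 0% give 200/4 = 50%, which fails. The outcome depends on whether the eCRF generates records after treatment stops.

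**Route into the PP result.** An early stopper without a Week 4 value influences the Week 4 contrast only through earlier visits in the MMRM. The influence is direct if a Week 4 value exists. One example is an unscheduled assessment on Days 23 to 28, which SAP Table 4 assigns to Visit 6 when no scheduled measurement is available.

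**The case against.** The strongest reply is that the formula is itself an answer. Averaging over the records present measures compliance while on treatment, which is a defensible definition, and neither document says the 80% refers to the full course. On that view the percentages above hold the plan to a standard it never set. This stands in part. A reader might infer that the SAP contradicts the protocol, or that the formula is simply wrong, but Protocol 9.1.2 gives no base, so neither reading is supported. What remains is that on-treatment compliance alone, with no exposure floor, lets a one-week subject count as per protocol, and the SAP does not say this is intended.

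Second, the eCRF is not shown. Protocol 8.11.1 and 8.11.3 tie the site's assessment to tube weights and diaries, and stopping early may produce a No record with a low percentage. That is possible, and it is why the claim is that such a subject can enter PP, not that every such subject will.

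Third, the case can be seen. SAP 7.1 tabulates discontinuation reasons and population counts by treatment, and Listings 16.2.3 and 16.2.5.3 cover analysis populations and missed doses. This helps a reader identify affected subjects but does not change who is in PP.

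Finally, the 16% dropout allowance might tempt a reader to infer that about 13 of 84 subjects (0.16 × 84 = 13.4) would be affected. The documents do not support that. The 16% is a planning figure, dropouts need not stop by Day 22 or have only Yes records, and it is not an upper bound either.

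**Conclusion.** The point holds as a minor one. As SAP 5 and 6.1.7 are written, a subject who stops by Day 22 with only Yes records scores 100% and can enter PP with less than 80% of the planned doses, and as little as 8/31 = 25.8% after one week. This rests on the literal formula and on there being no low enough later No record and no finding of serious deviation. The Day 22/23 boundary is the same on the 31- and 28-dose counts.

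The mITT primary analysis is untouched. The PP repeat is supportive, the effect on it is mostly indirect, and the number of subjects affected cannot be derived from the documents. Nothing here shows that the PP estimate would be biased in a particular direction.

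**What to change.** Before unblinding, adopt one of two rules for PP membership:

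1. Replace the record average with 100 × doses taken (the SAP 6.1.7 count) / doses planned for the full course, capped at 100%, and apply the 80% cut-off to it. The denominator must be the full course. The SAP's expected doses run only to the last treatment, so using them would again give an early stopper 100%. The cap covers visits in the ±1 day window: full adherence ending on Day 29 gives (29 + 3)/31 = 103.2%.
2. Keep the record average, call it on-treatment compliance, and add a separate minimum-exposure criterion to SAP 5.

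Under either rule, use the same dose count throughout, after the sponsor reconciles the twice-daily dosing on three days (31 doses) with once daily for 28 days (28 doses). The choice can change membership. A completer with six missed doses has 25/31 = 80.6% or 22/28 = 78.6%. Mixing the counts would pass a Day 21 stopper at 23/28 = 82.1%.

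State in the rule how interruptions permitted by Protocol 8.11.2 are counted, using only data the CRF collects. If seven withheld doses (not spanning Day 14) count as missed, an otherwise adherent completer has 24/31 = 77.4% (21/28 = 75.0%), so the rule should not leave this open.

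Cost: one SAP definition or criterion, built on a dose count already derived. PP becomes somewhat smaller and loses early stoppers, including tolerability withdrawals. That is post-randomisation selection and should be acknowledged when PP is read as supportive.
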